2.3 Exploratory Objectives

- 2.3.1 To evaluate the acceptability of anal cancer screening among HIV-positive women.
- 2.3.2 To collect data on quality of life and health care costs (including non-direct health care costs and time costs) for an economic evaluation of the cost-effectiveness of anal cancer screening strategies in HIV-positive women.

3.0 PARTICIPANT SELECTION

3.1 Inclusion Criteria

- 3.1.1 Women age 18 and older. “Women” is defined as persons documented as female at birth. Younger women are not included as anal cancer is a disease of adults.
- 3.1.2 HIV positive. HIV-1 infection, as documented by any federally approved, licensed HIV rapid test performed in conjunction with screening (or ELISA, test kit, and confirmed by Western blot or other approved test). Alternatively, this documentation may include a record demonstrating that another physician has documented the participant's HIV status based on either: 1) approved diagnostic tests, or 2) the referring physician's written record that HIV infection was documented, with supporting information on the participant's relevant medical history and/or current management of HIV infection.
- 3.1.3 Karnofsky performance status $\geq 70\%$.
- 3.1.4 Absolute neutrophil count ≥ 750 cells/mm³ within 120 days of study entry.
- 3.1.5 Platelet count $\geq 75,000$ cells/mm³ within 120 days of study entry.

3.2 Exclusion Criteria

- 3.2.1 Current or history of anal or peri-anal carcinoma.
- 3.2.2 History of anal HSIL cytology or histology; or anal cytology result with “ASCUS, cannot exclude HSIL.”
- 3.2.3 Known permanent or irreversible bleeding disorder, or any illness that, in the opinion of the clinical investigator, would contraindicate any biopsy of the anal canal.
- 3.2.4 For women able to conceive, evidence of pregnancy by a positive urinary pregnancy test within 72 hours prior to study entry. Pregnant women are excluded from enrollment in this study because of concerns about performing HRA during pregnancy.
- 3.2.5 Serious medical or psychiatric illness that in the opinion of the site Investigator will interfere with the ability of the participant to give informed consent or adhere to the protocol.
- 3.2.6 Ongoing use of anticoagulant therapy other than aspirin, clopidogrel, or non-steroidal anti-inflammatory drugs (NSAIDS).
- 3.2.7 Inability to provide informed consent.
- 3.2.8 Treatment of anal and/or perianal HPV associated disease (i.e., condyloma or low-grade AIN) within 4 months of study entry.

3.3 Number of Study Participants to be Enrolled

3.3.1 Proposed sample size

This study will enroll 300 participants.

3.3.2 Accrual rate

Approximately 20 participants per month.

3.4 Study Enrollment Procedures

Sites must have this protocol approved by the reviewing Institutional Review Board (IRB) and be registered for study participation with the AMC Operations and Data Management Center (ODMC) before they may enroll participants.

3.4.1 Enrollment

After the participant has signed informed consent, screening evaluations have been performed, and the participant is determined to be eligible, the participating site will complete the protocol-specific eligibility checklist and enroll the participant into AMC-084 (on-line via AdvantageEDCSM). Enrollment should occur no more than 1 week prior to Visit 1 (enrollment 1 day prior to or on the day of Visit 1 is strongly encouraged). Once the eligibility checklist is submitted, a system generated confirmation email will be sent to the enroller upon successful completion of the participant enrollment. If the on-line system is inaccessible, the site should notify the AMC ODMC (via email at [contact] or via phone at [contact]) for further instructions.

Participants must be enrolled into AMC-084 prior to initiating the study.

3.4.2 Screen failure

If a participant does not meet the eligibility criteria or refuses to take part in the study, a tracking sheet will be maintained locally on the number of participants eligible, approached, and enrolled (no PHI will be included).

4.0 CLINICAL AND LABORATORY EVALUATIONS

4.1 Schedule of Evaluations

Participants in the study will follow schedule of evaluations found in [Appendix I](#), Schedule of Evaluations.

4.2 Timing of Evaluations

4.2.1 Screening

Screening evaluations must occur prior to the participant starting any study procedures.

The screening and enrollment visit may be combined if the requisite laboratory results are available through routine clinical care.

In addition to data being collected on participants who enroll into the study, demographic data and reasons for screening failures (that are available) will be captured in a screening log.

4.2.2 On-study evaluations

Evaluations must occur after participant registration. Study visits must be scheduled on the weeks indicated in the Schedule of Evaluations ([Appendix I](#)) from -14 days to +160 days for visits 2-5 for the duration of the participant's participation. For visit 1, all study evaluations should be completed within 50 days before the enrollment visit.

4.3 Special Instructions and Definitions of Evaluations

All clinical and laboratory information required by this protocol is to be present in the source documents. All data requested by the study should be recorded in the source documents. All stated evaluations will be entered on the appropriate case report form (CRF) via the AdvantageEDCSM Internet Data Entry System unless otherwise specified. Quality assurance of data should follow the standards prescribed by the AMC.

4.3.1 Medical/medication history

Medical history

- CDC HIV risk categories and history of AIDS defining conditions
- History of treatment for HSIL of the cervix (CIN2,3) or cervical cancer
- History of treatment for HSIL of the vulva (VIN2,3) or vulvar cancer
- History of prior anal cancer screening with cytology or HRA
- History of pelvic radiation
- History of splenectomy
- Presence of chronic hepatitis B or C
- Year of HIV diagnosis
- Nadir CD4 count (if known)
- Allergies to any medications, including lidocaine, shellfish, or contrast agents
- Previous history of AIDS-defining opportunistic infection
- Listing of other past medical history
- Topical or surgical treatment of HPV-related disease

- History of prior cervical cytologies or biopsies in the past 2 years, and most severe prior cervical cytology and biopsy results (if available)
- History of prior anal cytologies or anal biopsies
- History of systemic cytotoxic chemotherapy and/or radiation (other than pelvic radiation)

A medication history must be present in source documents, including:

- Current and past ART regimens
- Actual or estimated start date of each agent that is part of the current cART therapy
- History of any prescription medications, immune modulating herbal supplements, and over the counter medication taken within 14 days of study entry
- History of HPV vaccination

4.3.2 Concomitant medications/antiretroviral medication modifications

Concomitant medications

Use of any systemic antineoplastic or immunomodulatory treatment, systemic corticosteroids, investigational vaccines, interleukins, interferons, growth factors, or intravenous immunoglobulin (IVIG) should be documented in the CRFs.

Any prescription medications that are not listed above that have been initiated since the last report should be documented in the source documents only. If the participant receives any dose of a HPV vaccine while on study, this must be documented in the source and reported in the CRFs.

Antiretroviral medications

Any modifications to antiretroviral medications since the last report will be entered on the CRFs. Modifications would include more than 14 consecutive days of missed antiretroviral medications. Modifications do not include change in current antiretroviral medication dose or formulations.

4.3.3 Nadir CD4+ cell count

The participant's prior nadir CD4+ cell count (absolute value and date) should be documented, when possible, with a copy of the nadir CD4+ cell count report and entered on the CRF. If this documentation is not available, then participant recollection will suffice. For participants who do not know the exact nadir value and for whom there is no source documentation, then recall of the categorical nadir (e.g., < 50, < 100, < 200, 200-500, \geq 500 cells/mm³) will suffice. If unknown, then the category of "unknown" will suffice.

4.3.4 Clinical assessments

Targeted physical exam

This should be documented in the source documents only. A targeted physical examination is to include vital signs (temperature, pulse, and blood pressure) and assessment of Karnofsky Performance Status (KPS) ([Appendix II](#)). The rest of the

targeted exam is to be driven by any previously identified or new signs or symptoms including diagnoses that the participant has experienced since the last visit.

The vulvar and perianal area will be examined for signs of HPV-related lesions. The presence or absence of vulvar/perianal condyloma will be recorded on the CRFs. Anal cytology and digital anal/rectal exam (DARE) are performed at each study visit. HRA with biopsy of visible disease (in the anal canal or perianus) (or at least 2 random sites from 2 different quadrants, if no disease is visible) will be performed to assess anal HPV-associated disease at visits 1, 3, and 5. Exception: If the participant is pregnant at visits 3 or 5, the HRA with biopsy will be deferred.

The participant will have a cervical/vaginal speculum exam with cervical/vaginal cytology (for visit 1, the participant will need a specimen if not available from within the past 42 days) and HPV collected annually beginning with the initial assessment (Visit 1).

4.3.5 Research staff administered questionnaires

A member of the research staff will administer a questionnaire to the study participant at each study visit to determine her smoking status, recent sexual history, as well as questions to assess quality of life, acceptability of the procedure, ascertain costs to the participant associated with anal cancer screening. The estimated time to complete this questionnaire is 20 minutes. The questionnaire includes the EQ-5D-5L for quality of life,⁴¹ PHQ-4 for anxiety and depression,⁴² the faces rating scale,⁴³ medication adherence,⁴⁴ acceptability of screening procedures,⁴⁵ sexual behaviors,²⁹ and personal health care cost information,⁴⁶ as well as adapted questions on self reported HIV medication adherence⁴⁶ and women's experience with colposcopy.⁴⁶ The baseline questionnaire ([Appendix XIII](#)) is administered at visit 1. The follow-up questionnaire (an abbreviated version of the baseline questionnaire) is administered at each subsequent visit (see [Appendix XV](#)).

4.3.6 Telephone follow-up questionnaire

The telephone follow-up questionnaire ([Appendix XIV](#)) may be conducted as a study visit if preferred by study staff or study participant. Each study participant will be contacted by the research coordinator/study nurse 1-5 weeks after each HRA procedure to:

- Administer a brief questionnaire assessing perceptions/acceptability of the HRA; and,
- Review the results from the HRA (cytology and biopsies).

4.3.7 Clinical and laboratory evaluations (See [Appendix I](#) for timing of evaluations)

- Anal cytology (See [Appendix III](#), Anal Sampling Procedures)
- Anal HPV studies (See [Appendix III](#) and [VII](#), HPV Specimen Collection and Shipping)
- Cervical cytology (See [Appendix V](#), Cervical Sampling Procedures)
- Cervical HPV studies (See [Appendix V](#) and [VI](#))
- Digital anal/rectal exam (DARE)

- High resolution anoscopy (HRA) with biopsy (See [Appendix IV](#))
- Blood collection for donation to the AIDS and Cancer Specimen Resource (ACSR) (two 8.5 ml yellow top tubes at ANY VISIT if the participant consents to donation)
- Laboratory test results from within 120 days of enrollment include the following:
 - Absolute neutrophil count
 - Platelet count
 - HIV viral load: Viral load studies will be performed using an assay with a limit of detection of 75 copies/ml or less (visits 1 and 5 only)
 - T cells: CD4 counts and percentages will be quantified (visits 1 and 5 only).
- Pregnancy test for women who can conceive: Pregnancy test (urine HCG) will be performed (and results obtained) within 72 hours of the enrollment visit, at Visit 3 (12 months), and at Visit 5 (24 months)

4.3.8 Evaluations during pregnancy

Any participant who becomes pregnant while on study will remain on study, and resume normal procedures once the pregnancy resolves. While pregnant, the HRA procedures may be omitted due to discomfort to the participant and an absence of data on the effect of these procedures on a developing fetus. Anal cytology sampling procedures may be omitted at the preference of the participant and the provider, and cervical cytology procedures may still be performed if required for the participant's medical care. Participants will resume all visits and procedures after resolution of the pregnancy. Any visits or procedures that are missed for this reason should be reported as missed visits and/or forms in AdvantageEDC, as appropriate.

4.4 Pathology Review

4.4.1 Initial pathology reading:

The specimens will first be sent to the local site's pathology department for processing and pathology interpretation. Each cytology and histology specimen will be assigned a unique accession number in the GlobalTraceSM specimen tracking system for data reporting purposes and for subsequent consensus pathology assessments.

Anal and cervical cytology specimens will be assigned a reading according to the current Bethesda System terminology:

- Negative for intraepithelial lesion or malignancy (NILM)
- Atypical squamous cells of undetermined significance (ASC-US)
- Low-grade squamous intraepithelial lesion (LSIL)
- High-grade squamous intraepithelial lesion (HSIL)
- Atypical squamous cells, cannot exclude HSIL (ASC-H)
- Atypical glandular cells (AGC)
- Cancer, specify squamous cell or adenocarcinoma

Anal histology specimens will be assigned a reading as per the CAP-ASCCP LAST Project terminology

- Benign/Reactive: squamous metaplasia; etc
- LSIL (condyloma OR AIN1)
- HSIL (AIN2, AIN2/3, or AIN3)
- Cancer, specify squamous cell or adenocarcinoma

Cytology and histology readings from the local cytopathology laboratories will be reported in the appropriate CRF in AdvantageEDCSM.

4.5 Consensus Pathology Review

All anal histology slides taken during Visits 1-5 will be submitted to the AMC Biorepository for central pathology review. See [Appendix VI](#) for details.

4.6 Follow-up for Abnormal Results

Clinical management for all study participants will be based on the local pathology interpretation. However, if the consensus pathology review is significantly different from the local pathology review, that information will be communicated to the clinical site to aid in patient management.

Anal

- If the anal cytology shows HSIL or ASC-H and no corresponding anal or perianal HSIL was found on HRA, then the participant should undergo another HRA in 3-6 months.
- Further evaluation and/or treatment recommendations will be made according to HRA findings (See [Appendix IX](#) for recommendations regarding further evaluation and/or treatment).

Cervical

- Participants with abnormal cervical cytology should be referred for colposcopy as per ASCCP management guidelines (See [Appendix IX](#)).

STUDY VISITS: (i.e., 6 month visits) participants will remain on schedule for data collection regardless of any interval visits for HRA, colposcopy, or treatment procedures (e.g., for symptomatic condyloma or HSIL of the cervix, CIN2, 3).

Results from any abnormal follow-up and any interval treatment procedures will be recorded in the CRF at the subsequent scheduled study visit.

4.7 Early Study Discontinuation Procedures

An Early Discontinuation form will be completed for all early study discontinuations to document the reason for early discontinuation.

5.0 CRITERIA FOR DISCONTINUATION

5.1 Early Study Discontinuation

- Diagnosis of histologic HSIL on any anal biopsy or cancer of the anus by either the local pathologists or the central pathology review at any time (including the enrollment visit). Only participants with benign or LSIL diagnoses on ALL anal biopsies at each visit will be allowed to continue in the study. Participants who have only cytologic HSIL diagnoses are permitted to continue on study as long as histology results do not show HSIL.
- Request by participant to withdraw from the study.
- Request of the primary care provider if s/he thinks the study is no longer in the best interest of the participant.
- The participant is judged by the Investigator to be at significant risk of failing to comply with the provisions of the protocol as to cause harm to self or seriously interfere with the validity of the study results.
- At the discretion of the AMC, IRB, Office for Human Research Protections (OHRP), or NCI.
- Clinical reasons believed life-threatening by the investigator.

6.0 ADVERSE EVENT REPORTING

Adverse event (AE) monitoring and reporting is a routine part of every clinical trial. The following list of AEs ([Section 6.1](#)) and the characteristics of an observed AE ([Section 6.2](#)) will determine whether the event requires routine reporting (via AdvantageEDCSM).

The CTEP Version 5.0 of the NCI Common Terminology Criteria for Adverse Events (CTCAE) will be utilized for AE reporting. The CTEP Version 5.0 of the CTCAE is identified and located on the CTEP website at

http://ctep.cancer.gov/protocolDevelopment/electronic_applications/ctc.htm.

All appropriate treatment areas should have access to a copy of the CTEP Version 5.0 of CTCAE.

6.1 Expected Adverse Events Related to the Study Procedures

Anal cytology collection, HRA, and anal biopsy

- Participants will likely experience pressure and urgency to defecate during the anal cytology collection and HRA. Participants may experience discomfort during the injection of local anesthetic (if used). There may be mild to moderate intra- and post-procedural pain for up to 2 weeks. Participants sometimes require pain medication post-procedure. Rarely, this pain can be severe or last longer than 2 weeks.
- Mild bleeding and discharge is relatively common after the procedure and may occur up to 2 weeks after the biopsy is taken. Rarely, there can be severe bleeding occurring 1-2 weeks post-procedure that is severe enough to prompt an evaluation at the emergency room.
- There is a slight risk (<1%) of infection or abscess post-procedure requiring antibiotics.

6.2 Classification of Adverse Events by Severity and Relationship

- 6.2.1 Adverse Event: Any unfavorable and unintended sign (including an abnormal laboratory finding), symptom, or disease temporally associated with the use of a medical treatment or procedure regardless of whether it is considered related to the medical treatment or procedure (attribution of unrelated, unlikely, possible, probable, or definite).
- 6.2.2 Life-threatening Adverse Event: Any AE that places the participant or participant, in view of the Investigator, at immediate risk of death from the reaction.
- 6.2.3 Serious Adverse Event (SAE): Any AE occurring at any dose that results in any of the following outcomes: Death, a life-threatening AE, inpatient hospitalization or prolongation of existing hospitalization, a persistent or significant disability/incapacity, or a congenital anomaly/birth defect.
- 6.2.4 Please note for hospitalization – All hospitalizations (or prolongation of existing hospitalization) for medical events equivalent to CTCAE Grade 3, 4, 5 must be reported regardless of the requirements for Phase of study, expected or unexpected, and attribution. For example, do not report an admission for pharmacokinetic sampling, but do report an admission for a myocardial infarction.
- 6.2.5 Toxicity: Toxicity is a term NOT clearly defined by regulatory organizations. Toxicity has been described as an AE that has an attribution of possibly, probably

or definitely related to investigational treatment. To minimize confusion the NCI would recommend that the term toxicity NOT be utilized for AE reporting purposes. The CTCAE continues to use the term ‘toxicity’ because of familiarity.

- 6.2.6 Unexpected Adverse Event: Any AE that is not listed in available sources including the package insert, the Investigator’s Brochure, or the protocol.
- 6.2.7 CTEP Adverse Event Reporting System (CTEP-AERS): An electronic system for expedited submission of AE reports.
- 6.2.8 Attribution: The determination of whether an AE is related to a medical treatment or procedure. Attribution categories:
 - Definite – The AE is clearly related to the investigational agent.
 - Probable – The AE is likely related to the investigational agent.
 - Possible – The AE may be related to the investigational agent.
 - Unlikely – The AE is doubtfully related to the investigational agent.
 - Unrelated – The AE is clearly NOT related to the investigational agent.

6.3 Routine AE Reporting

All adverse events (AEs) of Grade 3 or greater severity that are possibly, probably, or definitely attributed to the study procedures will be recorded on the Adverse Event Form in AdvantageEDCSM. Only adverse events of Grade 3 or greater severity are required for safety monitoring and study analysis. Adverse Event Forms will not be required for Grade 1 and 2 AEs; these events will only require recording in source documents. Participants withdrawn from the study due to AEs will be followed by the Investigator until the outcome is determined and, when appropriate, additional written reports and documentation will be provided.

7.0 STATISTICAL CONSIDERATIONS

7.1 Sample Size

The primary objective of the study is to evaluate the sensitivity and specificity of the following methods for the detection of HSIL of the anus (as determined by consensus pathology): anal cytology, HPV hybrid capture 2, HPV mRNA assays (APTIMA) and Arbor Vita OncoE6 HPV test. Note that throughout this section, HSIL (of the anus) is defined as the local or consensus pathology interpretation of any anal biopsy. At the initial visit, all women will undergo an HRA-directed biopsy to determine if they have HSIL. Since HRA is considered the “gold standard,” the findings on HRA will determine whether a woman is classified as having HSIL or not. HSIL may be under-diagnosed due to operator error, thus the diagnosis of HSIL will be based on the procurement of at least 2 biopsies during HRA. HSIL will be thus be defined as having the diagnosis determined by either local pathologist or the consensus pathology on *any* anal biopsy at a given visit. Based on previous reports,⁴¹ it is anticipated that approximately 10% of women will have HSIL. The prevalence of HRA-proven HSIL can be estimated with a 95% confidence interval of +/- 3.3%.

For each of the methods of detection, the null hypothesis that the sensitivity is 50% can be tested against the alternative that sensitivity is at least 75% at the one-sided 0.05 significance level with power of 0.89 with 30 HSIL participants. The HPV test results from all three tests—APTIMA, HC2, and HPVE6E7—are all dichotomous, i.e., reported as either positive or negative (or unevaluable). With 270 women who are negative for HSIL on HRA, the null hypothesis that specificity is 50% can be tested against the alternative hypothesis that specificity is at least 65% at the one-sided 0.05 significance level with power of 0.99.

The novel methods of detection (HPV hybrid capture 2, HPV mRNA assays (APTIMA) and Arbor Vita Onco E6 HPV test) will be evaluated to determine if they improve sensitivity or specificity compared to routine anal cytology using McNemar’s test. With 30 HSIL women, a 20% increase in sensitivity with 25% of participants with discordant results can be detected at the one-sided 0.05 significance level with 78% power. With 270 women negative for HSIL, a 20% increase in specificity with 25% of participants with discordant results can be detected at the one-sided 0.05 significance level with 99% power. Positive and negative predictive values will be assessed for each method of detection.

To determine incidence of HSIL, we will use the information from the women whose initial HRA examination is negative for HSIL. If these women are followed for an average of 1.8 months, we would expect $1.8 \times 270 = 486$ person-years of follow-up. The table below shows the 95% Poisson confidence intervals for two levels of the underlying incidence of HSIL with 486 person-years of observation:

| Underlying incidence of HSIL per 100 person-years | 95% Poisson confidence interval (per 100 person-years) |
|---------------------------------------------------|--------------------------------------------------------|
| 2.06 | (1.11, 3.82) |
| 3.09 | (1.86, 5.12) |

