7.2 Primary Statistical Analyses

7.2.1 Primary analyses

To estimate the sensitivity and specificity of each of the methods of detection, the binomial proportion and its 95% confidence interval will be used. Among participants who are HRA positive for HSIL, McNemar's test will be used to compare routine anal cytology with each of the other methods of detection to determine if sensitivity in the diagnosis of HSIL is improved with the other methods. Similarly, among participants who are HRA negative for HSIL, McNemar's test will be used to compare routine anal cytology with each of the other methods of HPV detection to improve specificity. Positive and negative predictive values will be estimated for each method of detection.

The prevalence of HSIL will be estimated as the proportion of women who are HRA positive for HSIL at entry and its 95% confidence interval. Logistic regression analyses will be used to evaluate the association of potential risk factors (cervical HPV, abnormal cervical cytology, behavioral, and immunologic characteristics, such as plasma HIV-1 RNA, current and nadir CD4 count) with diagnosis of HSIL.

To estimate the incidence of HSIL among women who were HRA negative for HSIL at study entry, the Poisson rate and its 95% confidence interval will be estimated from the number of HSIL cases detected divided by the cumulative years of follow-up across these cases. Behavioral risk factors will be assessed by research staff administered surveys at each study visit. Included in these risk factors is the risk of ongoing sexual exposure to HPV in the study population. Logistic regression will be used to evaluate potential risk factors for incidence of HSIL.

To estimate the incidence of anal HPV among women who were negative for anal HPV at study entry, the Poisson rate and its 95% confidence interval will be estimated from the number of anal HPV cases detected divided by the cumulative years of follow-up across these cases. Logistic regression will be used to evaluate potential risk factors for incidence of anal HPV.

Analysis of the results of the Arbor Vita assay will be delayed after the primary analysis is performed using the results of the Hybrid Capture 2 and Aptima Assays, if the Arbor Vita assay is optimized to yield sufficient results from anal cytology specimens in the future.

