- 1) To differentiate between the H&E morphologic diagnosis of precancer (–IN 2 or –IN 3) and a mimic of precancer (e.g., processes known to be unrelated to neoplastic risk such as immature squamous metaplasia, atrophy, reparative epithelial changes, tangential cutting). Strong and diffuse block-positive p16 results support a categorization of precancerous disease.
- 2) To clarify a diagnosis of –IN2 in an H&E morphologic interpretation of –IN 2 (under the old terminology), which is a biologically equivocal lesion falling between the morphologic changes of HPV infection (low-grade lesion) and precancer. Strong and diffuse block-positive p16 results support a categorization of precancer. Negative or non-block-positive staining strongly favors an interpretation of low-grade disease or a non-HPV-associated pathology

Central pathology review

- Please review the MOP for central pathology slide shipping instructions and central pathology review.

For quality control, each site will submit all baseline histology study slides used for screening evaluation, including any stained slides, collected from the first six months after enrollment of the first study participant at a given study site. These slides should be batch shipped to the AMC Biorepository as soon as possible up to 9 months after enrollment of the first study participant at each study site. All anal histology slides taken during Visits 1-5 will also be submitted to the AMC Biorepository for central pathology review. The AMC Biorepository will distribute all slides except those originating from UCSF to [name] at UCSF for review, and will ship all slides originating from UCSF to Baylor College of Medicine for review. Central review from the participating pathologists will be returned to study sites within 6-8 weeks of receipt.

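### Does the mention of consensus pathology in Section 7.1 leave the HSIL reference standard undefined?

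*Combined protocol and SAP*

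**What the plan says.** Section 7.1 opens with the primary objective, which concerns "methods for the detection of HSIL of the anus (as determined by consensus pathology"). The next sentence states that, throughout the section, "HSIL (of the anus) is defined as the local or consensus pathology interpretation of any anal biopsy". The paragraph goes on to say that HRA is the gold standard and that HRA findings classify each woman. It notes that HSIL may be under-diagnosed, requires at least two biopsies for that reason, and closes the point by defining HSIL again as "the diagnosis determined by either local pathologist or the consensus pathology on" any anal biopsy at a given visit.

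Section 7.2.1, which lists the analyses, uses a shorthand: "Among participants who are HRA positive for HSIL, McNemar's test will be used to compare routine anal cytology with each of the other methods". It handles specificity in the same way among HRA-negative women. It names no reader.

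Section 5.1 ends participation for a woman with HSIL or anal cancer found "by either the local pathologists or the central pathology review at any time".

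Both readings will exist. Section 4.4 says that "Cytology and histology readings from the local cytopathology laboratories will be reported in the appropriate CRF", and Appendix VI says that "All anal histology slides taken during Visits 1-5 will also be submitted to the AMC Biorepository for central pathology review".

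**The concern.** In a diagnostic-accuracy study the reference standard decides who counts as diseased, so it should have one meaning. Here the sentence that states the primary objective names consensus pathology, while the definition after it accepts either reader. The women affected are those called HSIL locally but not centrally. Section 4.6 allows for the two readings to differ.

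The HSIL group is planned at about 30 women, so moving a few could shift sensitivity, predictive values, prevalence and the McNemar comparison of sensitivity. Because Section 7.2.1 names no reader and both readings will be on file, one might fear that the definition could be chosen after the results are seen.

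A second worry is that site laboratories report both the comparator cytology and the local histology, whereas the central reading is made elsewhere. For example, Appendix VI says that the biorepository "will ship all slides originating from UCSF to Baylor College of Medicine for review". A local-only HSIL call might therefore be less independent of the cytology than a central one.

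**Working it through.** **1. Which definition governs.** The wordings compare as follows.

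| Place | Reader rule |
|---|---|
| 7.1, objective sentence (parenthetical) | consensus |
| 7.1, next sentence, declared to hold throughout the section | local or consensus |
| 7.1, later in the same paragraph | local or consensus |
| 5.1, discontinuation | local or central |
| 2.2.1, objective | biopsy-proven, no reader named |
| 7.2.1, analyses | HRA positive or negative, no reader named |

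An explicit definition given twice outranks a descriptive aside. Section 7.2.1 sits under the same heading 7.0. Even if the declared scope were 7.1 alone, 7.1 itself says that HRA findings classify the woman, explains that this means biopsies read by either reader, and describes the same McNemar comparisons. The shorthand in 7.2.1 therefore carries the same meaning.

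**2. The plan's own figures.** The inputs from 7.1 are 300 women, 10% with HSIL (30 cases, 270 non-cases) and one-sided 0.05.

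- Sensitivity 50% against 75%, n = 30, exact binomial: reject at 20 or more positives. P(X ≥ 20 | 0.5) = 0.049 and P(X ≥ 20 | 0.75) = 0.894. Stated: 0.89.
- Specificity 50% against 65%, n = 270, exact binomial: reject at 150 or more. Power is above 0.999. Stated: 0.99.
- McNemar, n = 30, 25% discordant, difference 20 points (so 22.5% and 2.5%), z test without continuity correction, averaged over the number of discordant pairs: 0.776. Stated: 78%.

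The figures reproduce. Under the either-reader definition the 30/270 split stands, so none of them changes.

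**3. How far the two definitions could differ.** The documents give no rate of local-central disagreement, so this step is an assumed range. Take 30 either-reader cases, k of them local-only. The test is positive in 75% of centrally confirmed cases, in 35% of non-cases, and in a proportion q of local-only women, with q from 35% to 75%.

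- Either-reader sensitivity = [0.75(30 − k) + qk]/30. Consensus-only sensitivity is 75% by assumption.
- Either-reader specificity is 65% by assumption. Consensus-only specificity = [270 × 0.65 + k(1 − q)]/(270 + k).
- Consensus-only prevalence = (30 − k)/300.

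| k | Either-reader sensitivity, q = 35% | Same, q = 75% | Consensus-only specificity, q = 35% | Same, q = 75% | Consensus-only prevalence |
|---|---|---|---|---|---|
| 0 | 75% | 75% | 65.0% | 65.0% | 10% |
| 3 | 71% | 75% | 65.0% | 64.6% | 9% |
| 6 | 67% | 75% | 65.0% | 64.1% | 8% |
| 9 | 63% | 75% | 65.0% | 63.7% | 7% |

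At k = 6 and q = 35%, test positives number 0.75 × 24 + 0.35 × 6 + 0.35 × 270 = 18 + 2.1 + 94.5 = 114.6. PPV is 20.1/114.6 = 17.5% under either-reader and 18/114.6 = 15.7% under consensus-only. Test negatives number 185.4. NPV is 175.5/185.4 = 94.7% and 179.4/185.4 = 96.8% respectively.

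The sensitivity gap is thus 0 to 12 points. The upper end needs 9 of 30 cases to be local-only and to test exactly like women without HSIL.

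**4. What a consensus-only analysis would cost.** With 27, 24 and 21 cases, exact power for 50% against 75% is 0.79, 0.77 and 0.74, and McNemar power is 0.73, 0.68 and 0.63. Part of the first fall, from 0.89 to 0.79, comes from discreteness: attained alpha drops from 0.049 to 0.026, and the normal approximation gives 0.90 and 0.86. If instead the anticipated 10% refers to consensus-only HSIL, the either-reader rule adds cases. With 33 to 42 cases, normal-approximation power is 0.92 to 0.97.

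**The case for a change.** The best case for a change is that the sentence stating the primary objective should not name a different reference standard from the one used, and that the correction is one phrase. Under the unfavourable assumptions the definition could also decide the sensitivity result. If local-only women test positive at 35%, the power of the plan's own rule (20 or more of 30) falls from 0.89 to 0.78, 0.61 and 0.41 at k = 3, 6 and 9. Both readings will be available, and a consensus-only repeat with a local-by-central table would need no new data.

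The textual point stands: the parenthetical does not match the definition. The rest carries less weight. A later switch to consensus-only would contradict two explicit definitions, so the choice is not open. The loss of power is what the either-reader rule would cost under assumed disagreement, and the documents cannot say whether k is 0 or 9. The shared-laboratory point is only a possibility, because the documents do not say whether one reader handles both specimens or is blinded. The repeat is a reasonable supplement that an analyst may add, but it does not correct a wrong rule.

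**Conclusion.** The mismatch is real but clerical. The operative reference standard is HSIL on any anal biopsy by the local or the consensus reading. That is a coherent choice in a paragraph concerned with under-diagnosis, and it agrees with who leaves the study under Section 5.1. An analyst would apply it in Section 7.2.1 without further instruction. Tidying the parenthetical would move no woman between groups and would alter no stated power. The difference of 0 to 12 points in sensitivity, with at most 1.3 points in specificity, describes a definition the plan does not adopt. It depends entirely on an assumed local-only share of 0 to 9 of 30 cases and an assumed test positivity of 35% to 75% in those women. This reading relies on the either-reader definition reaching Section 7.2.1, which both the scope of that definition and the use of HRA classification within 7.1 support. No change to the plan is called for.
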